- 2. Presence of a preexisting significant GI condition that does not have a presumed causal relationship with MPA

- 3. Evidence of any GI disorder induced by an infection, underlying medical condition, or concomitant medication other than MPA
- 4. eGFR<35 ml/min at time of possible conversion
- 5. Proteinuria >1 gram/day at time of possible conversion
- 6. Profound bone marrow suppression at the time of possible conversion as defined as:
 - Hemoglobin <10 g/dL
 - WBC <3 K/cumm
 - Platelets <100 K/cumm
- 7. Wound healing issues at time of possible conversion (eg, wound dehiscence, wound infection, incisional hernia, lymphocele, seroma)
- 8. Elevated total cholesterol (>350 mg/dL) and/or triglycerides (>500 ng/dL) at time of possible conversion
- 9. Hypersensitivity to everolimus, sirolimus, or other rapamycin deriviatives

Investigational and reference therapy:

Investigational therapy

- Everolimus tablets 0.25 mg, 0.5 mg, and/or 0.75 mg

Study design: Patients will be selected if they experience non-infectious GI adverse effects within the first 12 months post transplant. Following selection they will have a baseline screening and enrollment with a complete medical history, medication history, vital signs and labs (including tacrolimus and everolimus levels). In addition, their adverse effects and GSRS and GIQLI will be recorded. After enrollment they will have medication history, vitals, labs (including tacrolimus), and GSRS/GIQLI and adverse events recorded at months 1, 3, 6, 9, and 12 (excepting GSRS and GIQLI at month 9).

Efficacy assessments:

- Change in GSRS from baseline to month 3
- Change in GSRS subscores from baseline to month 3
- Changes in GSRS from basline to month 6 and 12
- Change in GIQLI from baseline to month 3
- Change in GIQLI subscores from baseline to month 3
- Changes in GIQLI from baseline to month 6 and 12

Other assessments:

- BPAR rates during study (compared with historical control)
- eGFR by MDRD4 from baseline to month 12 (compared to historical control)
- Death (compared with historical control)
- Graft loss (compared with historical control)

Data analysis:

Data for primary and secondary efficacy will be compared using a paired T-test.

Background

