This study will be conducted over a 2-year period, during which patients will be enrolled through the first year, and follow-up of a minimum of 1 year will be collected on each patient. Interim analyses will be conducted at 6-months or upon enrollment of 15 patients (whichever is earliest). The interim analyses will assess the rate of study drug discontinuation due to non-efficacy (as determined by nephrologist). If more than 5 patients (33%) have discontinued drug due to non-efficacy, the study will be terminated. Additionally, any other problems or safety signals will be addressed by the research team at this time.

Subjects meeting criteria will be asked to sign an informed consent, and upon execution of informed consent this will be considered study day 1. They will examined on study day 1 including a medical history, medication history, vital signs, height, weight, and BMI. Subjects will complete GSRS and GIQLI surveys, report adverse effects, and complete laboratory tests, including tacrolimus levels. Subjects will have 5 additional visits during the study period, which will include a medication history, vital signs, height/weight/BMI, adverse effect recording, GSRS and GIQLI (excepting visit 5), laboratory work including tacrolimus and everolimus levels, and reporting of infectious symptoms. These visits will occur at the end of months 1, 3, 6, 9, and 12.

Figure Error! No text of specified style in document.-1 St

Study design

Population

We intend to include patients who have received kidney transplant at the Washington University/Barnes-Jewish Hospital transplant program in the year prior to enrollment who are exhibiting signs of non-infectious GI toxicity determined by the treating physician to be secondary to MPA. In total, 30 candidates will be enrolled and treated with conversion from MPA to EVR. We anticipate a dropout rate of 20%, and expect that 24 patients will complete a full year of study drug. Severity of GI adverse effects will be assessed using the GSRS and GIQLI scales, but no specific severity threshold will be used to enroll patients. The study will be conducted largely on outpatients, but patients may be initially enrolled during inpatient stays.

Inclusion criteria

Patients eligible for inclusion in this study have to fulfill all of the following criteria:

- 1. Patients must give written informed consent before any assessment is performed.

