- 2. Adult kidney transplant recipients at Washington University/Barnes-Jewish Hospital
- 3. Experiencing GI toxicity from MPA as determined by the treating physician within 12 months postrenal transplant
- 4. On standard immunosuppression with tacrolimus and prednisone

Exclusion criteria

1. Dual organ or kidney after another solid organ transplant

2. Presence of a preexisting significant GI condition that does not have a presumed causal relationship with MPA

3. Evidence of any GI disorder induced by an infection, underlying medical condition, or concomitant medication other than MPA

- 4. eGFR<35 ml/min at time of possible conversion
- 5. Proteinuria >1 gram/day at time of possible conversion
- 6. Profound bone marrow suppression at the time of possible conversion as defined as:
 - Hemoglobin <10 g/dL
 - WBC <3 K/cumm
 - Platelets <100 K/cumm

7. Wound healing issues at time of possible conversion (eg, wound dehiscence, wound infection, incisional hernia, lymphocele, seroma)

8. Elevated total cholesterol (>350 mg/dL) and/or triglycerides (>500 ng/dL) at time of possible conversion

9. Hypersensitivity to everolimus, sirolimus, or other rapamycin deriviatives

Treatment

Investigational and control drugs

Patients enrolled in the trial will receive everolimus tablets at a starting dose of 1 mg PO BID, which will be dispensed in 0.5 mg tablets in blister-packages of 60-each.

Treatment arms

This will be a single-arm study. All patients enrolled with be assigned to the everolimus arm. We will include an observational retrospective analysis of those on AZA-based immunosuppression for comparison of risk of acute rejection, chronic rejection, graft-loss, and death, but these patients have already been allocated treatment and completed follow-up.

Treatment assignment

This will be a single-arm study. All patients enrolled with be assigned to the everolimus arm.

Treatment blinding

This will be an open-label study. All participants including researchers, subjects, and analysts will be aware of treatment allocation.

Treating the patient

Patient numbering

Patients will be numbered sequentially from 1 through 30 based on the order they complete consent and enrol in the study

Dispensing the study drug

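### The triglyceride limit in exclusion item 8 is given in ng/dL in both places where it appears, an apparent unit error in an operative eligibility threshold (minor)

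*Combined protocol and SAP*

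**What the plan says.** The lipid criterion appears twice, each time as item 8:

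- **Exclusion criteria (main protocol):** "Elevated total cholesterol (>350 mg/dL) and/or triglycerides (>500 ng/dL) at time of possible conversion".
- **Protocol synopsis, Key exclusion criteria:** the same limit, "triglycerides (>500 ng/dL) at time of possible conversion".

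Three other places bear on how the criterion is used:

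- **Population:** "In total, 30 candidates will be enrolled and treated with conversion from MPA to EVR". The synopsis gives 25 instead of 30.
- **Patient demographics/other baseline characteristics**, under Visit schedule and assessments: a subject may start study drug once all inclusion and exclusion criteria are met.
- **Sample size calculation:** the 60 historical controls are to be drawn from patients who also met the stated inclusion and exclusion criteria.

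No other section gives a triglyceride limit or a unit for one.

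**The concern.** The two halves of one criterion use mass units that differ by a factor of one million, and nothing elsewhere in the document settles which was meant. The limit is not background text. It is compared with a laboratory result to decide whether a patient may be dosed, and it applies to both sides of the historical comparison of rejection, graft survival, patient survival and infection.

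What is at stake is whether the criterion can be applied and audited. Staff who check a result against the printed limit cannot apply it sensibly. Staff who substitute another unit are using a threshold that the approved text does not contain, although the Protocol Amendments section requires any change to be made by written amendment.

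**Working it through.** The threshold is stated, not derived, so there is no calculation in the plan to reproduce. The check is a unit conversion followed by a comparison with the rest of the text.

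**Inputs**

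- Triglyceride limit: 500 ng/dL (item 8, both lists).
- Cholesterol limit in the same line: 350 mg/dL (item 8, both lists).
- Planned enrolment: 30 (Population) or 25 (synopsis).
- Historical controls: 60 (Sample size calculation).
- Conversion: 1 mg = 1,000,000 ng.

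**Step 1: convert the limit.** 500 ng/dL ÷ 1,000,000 ng/mg = 0.0005 mg/dL.

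**Step 2: compare it with its neighbours.**

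- Same number in mg/dL: 500 ÷ 0.0005 = 1,000,000 times higher.
- Cholesterol limit: 350 ÷ 0.0005 = 700,000 times higher.

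**Step 3: ask who would exceed it.** The documents give no triglyceride values, so this step needs an assumption: that patients' results lie above 0.0005 mg/dL. The margin is wide. A result of only 1 mg/dL would be 1 ÷ 0.0005 = 2,000 times the limit, so the conclusion is the same for every value from there upwards. The two lipid limits are joined by and/or, so exceeding the triglyceride limit is enough to exclude a patient whatever the cholesterol result.

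**Step 4: set the literal reading beside the rest of the plan.**

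| Text | Literal limit of 0.0005 mg/dL |
|---|---|
| Item 8 concerns elevated lipids | Every realistic value would count as elevated |
| 30 patients to be enrolled (25 in the synopsis) | 0 eligible |
| 60 controls meeting the same criteria | 0 eligible |

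The literal reading contradicts all three, so the printed unit cannot be what was meant.

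**Step 5: check whether any calculation depends on it.** The sample size rests on a change of 12 GSRS points, a standard deviation of 18, a 0.05 significance level and 20% dropout. A two-sided paired t-test with those inputs has power 0.807 at n = 20, and 20 ÷ (1 − 0.20) = 25, which is the stated figure. No lipid quantity enters. The planned paired t-tests, chi-squared tests, ANOVA and Kaplan-Meier estimates do not use the limit either.

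**The case against.** The strongest reply is that this is a visible one-letter slip that nobody would apply literally. The criterion concerns elevated values, the unit beside it is mg/dL, and the protocol plans to enrol 30 patients. The study has one center, with study-visit laboratories run on-site, so sites cannot differ in how they read the unit. The two lists are near-verbatim copies, down to a shared misspelling in item 9, so the repetition is one error pasted twice rather than two independent errors. All of this stands, and it is why the point is minor.

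It is also possible that the letter was misread when the text was taken from the PDF. That cannot be fully excluded. However, the same letter would have had to be misread in both lists while the mg/dL earlier in the same line came through correctly both times. An error in the source is the simpler explanation.

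A reader might infer three stronger conclusions, none of which the documents support:

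- **That the trial would in practice exclude every patient.** This follows only from literal application, which the wording of the criterion and the enrolment plan both rule out.
- **That every enrolled patient is a formal eligibility deviation.** No section defines deviations in a way that yields this result.
- **That the trial lacks a lipid safeguard specific to everolimus.** The protocol gives no reason for the lipid criterion, and its cholesterol half is unaffected.

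What the reply does not remove is that the printed limit gates dosing and control selection, and no other text corrects it.

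**Conclusion.** The point holds as an apparent unit error in an operative eligibility threshold, present in both places where the threshold is stated. As written, the limit is 0.0005 mg/dL, lower by a factor of 1,000,000 than the same number in mg/dL, and it is incompatible with the criterion's own wording and with the planned enrolment. It affects the definition of both the conversion patients and the historical controls.

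Severity is minor. Staff would probably read past the error, and the sample size and analyses are unaffected.

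The conclusion rests on one assumption from outside the documents, that real triglyceride results exceed 0.0005 mg/dL, and on the extracted text matching the source PDF. The expectation that staff would read past it is a judgement, not something that the protocol states.

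**What to change.** The sponsor should confirm the intended unit and limit for triglycerides, then correct item 8 in the synopsis and in the main exclusion list together, in one amendment, so that the two agree and can be applied and audited as written. The same confirmed criterion should be used when the historical controls are selected. Which value is right is for the sponsor to say.

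The cost is a wording change in two places, plus the approvals that any amendment needs. Nothing has to be recalculated.

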Study drug will be dispensed by the Barnes-Jewish Hospital Investigational New Drug (BJH IND) pharmacy, [name] They will receive a supply of 360 tablets of the 0.5 mg strength during their first study visit with a prescription label as outlined below.

Study drug supply, storage and tracking

Study drug supply with be shipped to the IND pharmacy, and it will be stored within an automated dispensing cabinet system (PYXIS), accessible only to the BJH IND pharmacy staff. Dispensing logs will be maintained by the BJH IND pharmacy staff, and the study team will track doses assigned for each patient during and following the titration period.

Instructions for prescribing and taking the study drug

Upon enrollment, patients will be instructed to begin taking 2 tablets by mouth twice daily beginning the evening following enrollment. Patients will continue taking everolimus twice daily through the study duration until the morning of the final visit (visit 6- end of month 12). The dose will be adjusted based on everolimus trough levels (as measured in whole blood using liquid chromatography and mass spectrophotometry methods) to target an everolimus level between 3 and 8 ng/mL. These assessments of everolimus levels will be made on a q2week schedule initially.

Permitted study drug dose adjustments and interruptions

As above, patients will have regular assessments of their everolimus levels. The first level assessment will be taken no sooner than 3 days following administration of the first dose. Any dose changes will lead to follow-up levels no sooner than 3 days following dose adjustment. The trough goal for EVR for the study is between 3 and 8 ng/mL. Levels below 3 ng/mL should result in a dose adjustment equaling double the previous dose. Levels above 8 ng/mL should result in a decrease in dose by 0.25 mg per dose. Changes to dose may also be made at treating physician discretion.

Additionally, tacrolimus levels will be assessed and doses adjusted upon these levels, targeting a trough level between 2 and 5 ng/mL. Adjustments to TAC doses may be made at treating physician discretion.

Drug interruptions may occur at the discretion of treating physician for severe or opportunistic infection, evidence of adverse effects requiring interruption (such as pulmonary infiltrates), or during periods of severe illness where oral route is unavailable.

Other concomitant treatment

Stong inducers or inhibitors of CYP3A4/3A5 are prohibited.

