Visit schedule and assessments

Table 7-1 lists all of the assessments and indicates with an "x" the visits when they are performed. The day of enrollment will be considered to be study Day 1. Subjects will make scheduled study visits on Day 1, at the end of Months 1, 3, 6, and 12. Subjects who discontinue their study treatment regimen should be treated according to standard of care immunosuppression and return for the assessments indicated by X in Table 6-1. If they refuse to return for these assessments or are unable to do so, every effort should be made to contact them or a knowledgeable informant by telephone to determine the subject and graft status.

Table Error! No text of specified style		A550	essment	schedule	;	
	Screening	Treatment period (post-switch)				Final study visit
	And	Month 1	Month 3	Month 6	Month 9	Month 12
	Enrollment		-	•		
Visit	1	2	3	4	5	6
Medical history	Х					
Medication history	Х	Х	Х	Х	Х	Х
Vital signs	Х	Х	Х	Х	Х	Х
Height, weight, BMI	Х	Х	Х	Х	Х	Х
Informed consent	Х					
Dispense medication and/or instruct subject regarding use	X					
Record adverse events	Х	Х	Х	Х	Х	Х
GSRS and GIQLI instruments	Х	Х	Х	Х		Х
Clinical laboratory tests	Х	Х	Х	Х	Х	Х
Tacrolimus/everolimus trough levels	Х	X	Х	Х	Х	Х
**Trough concentrations to be drawn twice weekly upon initiation and/or dosage change until therapeutic goal level is obtained						
Evidence of bacterial, viral, and fungal infection **At the following visits and at any point such infection is reported to a physician, transplant coordinator, or study coordinator	X	X	x	X	X	X

Table Error! No text of specified style in document.-1 Assessment schedule

Patient demographics/other baseline characteristics

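### Everolimus troughs after conversion are set at every 2 weeks in the dosing text but twice weekly until goal in the assessment-table footnote

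*Combined protocol and SAP*

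**What the plan says.** Three places in the protocol bear on when an everolimus trough is drawn.

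- **Instructions for prescribing and taking the study drug.** Doses are adjusted on whole-blood troughs towards 3-8 ng/mL. The section then says: "These assessments of everolimus levels will be made on a q2week schedule initially".
- **Permitted study drug dose adjustments and interruptions.** Two timing limits are given: "The first level assessment will be taken no sooner than 3 days following administration of the first dose", and "Any dose changes will lead to follow-up levels no sooner than 3 days following dose adjustment". A level below 3 ng/mL doubles the dose; a level above 8 ng/mL lowers it by 0.25 mg per dose. For the companion drug, "tacrolimus levels will be assessed and doses adjusted upon these levels, targeting a trough level between 2 and 5 ng/mL".
- **Visit schedule and assessments.** The section opens by saying that "Table 7-1 lists all of the assessments". The trough row of that table names tacrolimus and everolimus together and is marked at every visit, including month 1. Its footnote reads: "Trough concentrations to be drawn twice weekly upon initiation and/or dosage change until therapeutic goal level is obtained".

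**The concern.** The two frequency statements concern the same drug, the same measurement and the same period, since one speaks of the initial schedule and the other of initiation. One asks for a level every 2 weeks, the other for two a week until goal. Nothing in the protocol ranks them.

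The trough drives titration. Patients within a year of a kidney transplant come off MPA and start everolimus, with tacrolimus aimed at a 2-5 ng/mL trough. The Purpose and rationale section itself names rejection and graft failure as possible consequences of reducing MPA immunosuppression. If staff work from the dosing text, an out-of-range everolimus level may be found later than the table requires. The dose steps add to this: after a doubling, an overshoot could go unseen until the next scheduled level.

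**Working it through.** **Can the two statements be reconciled from the text?**

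1. *The footnote covers tacrolimus only.* No. Its row names both drugs, and everolimus is the one being initiated.
2. *The two-weekly rule applies only after goal is reached.* The wording fits this poorly: the sentence says the schedule holds initially, and it follows directly on the dose-adjustment rule.
3. *The 3-day limits decide it.* No. They give an earliest day and no latest day, so they are compatible with either schedule.
4. *The two-weekly wording is a slip for twice a week.* This is possible, but as written it means every 2 weeks and would still need correcting.

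**How far apart are they?** The plan gives no figure to reproduce. The inputs are the two frequencies, the 3-day minimum and twice-daily dosing, all from the protocol. My assumptions are that days count from the first dose, that every 2 weeks means at most 14 days to the next level, that twice weekly means every 3 to 4 days, and that a dose change is made on the day of the draw.

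With k dose changes already made, the latest day for the next level is 14(k+1) under the dosing text and 4(k+1) under the footnote.

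| Level | Latest day, dosing text | Latest day, footnote | Lateness, at most |
|---|---|---|---|
| First (k = 0) | 14 | 4 | 14 - 4 = 10 days |
| After one change (k = 1) | 28 | 8 | 28 - 8 = 20 days |
| After two changes (k = 2) | 42 | 12 | 42 - 12 = 30 days |

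The minimum lateness is zero in every row, because both rules allow a level 3 days after the first dose or a change.

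Doses taken before the first level, at two a day: 2 × 14 = 28 at the latest under the text, against 2 × 4 = 8 under the footnote.

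The month 1 trough is due under either reading and can shorten the third row. If that visit falls on day 31, which is 3 days after a change on day 28, the lateness is at most 31 - 12 = 19 days. If it falls on day 28, it coincides with the second two-weekly draw and shortens nothing.

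Required draws in 28 days for a patient never at goal: as few as 2 under the text (days 14 and 28), against 2 × 4 = 8 under the footnote.

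**The case against.** The strongest reply is that both rules can be met together. The dosing text permits early sampling, so a center that draws twice weekly until goal and then every 2 weeks during the early months breaks neither. On this view the protocol merely has a loose statement beside a stricter one triggered by initiation or a dose change. As a description of what careful staff could do, that stands. It does not remove the fault: the protocol never states this relation, and a reader of the dosing section alone would think a level every 2 weeks sufficient.

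A second reply is that the worst case requires staff to overlook the table. This has force. The table is introduced as listing all assessments, and its footnote holds the only tacrolimus sampling frequency outside the fixed visits, so staff at this single center need it anyway. Reliance on the two-weekly rule alone is therefore less likely. It remains possible, because neither fact is a rule of precedence. The physician's discretion to change doses does not set the sampling interval either.

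A reader might also subtract the footnote's earliest day from the text's latest and obtain 14 - 3 = 11, 28 - 6 = 22 and 42 - 9 = 33 days. Those figures overstate the lateness, because the footnote is still met on day 4, 8 or 12.

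**Conclusion.** The inconsistency is real and stands in current text. Its firm size is the first-level comparison: up to about 10 days' lateness, on the assumptions listed. The figures after dose changes are upper limits that also assume same-day dose changes; the documents give no turnaround time for the laboratory result.

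A reader might infer that patients will be under-immunosuppressed, or that rejection or toxicity will rise. The documents do not support that. They give neither the share of patients out of range at the 1 mg twice-daily starting dose nor any relation between the timing of levels and clinical events. Nor does the point reach the primary paired t-test, its alpha or the sample size, none of which depends on the sampling interval. The trough target and the dose steps are consistent throughout; only the required interval conflicts.

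Confidence in the textual mismatch is high. The weight is minor: it should be corrected, but it sits at the low end of such points.

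**What to change.** Replace the dosing-text sentence with one rule that matches the table: everolimus troughs are drawn twice weekly from initiation and after any dose change, no sooner than 3 days after the first dose or the change, until 3-8 ng/mL is reached, and then at a stated interval during the early period. Every 2 weeks would serve for that later interval, if this is what the present sentence was meant to cover. Put the same post-goal interval in the table footnote.

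The post-goal interval is a necessary part of the change. Under the footnote alone, a patient in range at the first draw has no further level required until the month 1 visit.

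The cost is one replaced sentence and a matching footnote addition in an amendment at a single center. Off-goal patients may have more draws than the dosing text alone requires, about 8 against as few as 2 in 28 days, but the table already requires all of them.

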At each study visit, with the exception of study visit #5, the will be administered by a member of the study team. Subjects will be interviewed by one of the investigators, and their responses will be recorded at each time point. The interviewer will be provided a sheet with each of the symptom areas, the associated questions, and the rating scale to conduct the interview. They will ask each question and read each potential response to the patient and circle the associated answer. These scores will be used to calculate their overall GSRS score, as well as the 5 sub-scores. The GSRS has been validated in numerous studies, including the initial study of the GSRS (Svelund J. *Dig Dis Sci.* 1988) which demonstrated validity and strong interrater reliability. It has subsequently been studied in the setting of kidney transplant recipients experiencing non-infectious GI adverse effects (Bolin P. *Transplantation 2007*). The scores in each of the domains (indigestion, diarrhea, constipation, abdominal pain, and reflux) will be recorded following the interview and will be compared longitudinally.

Gatrointestinal Quality of Life Index (GIQLI)

Following completion of the GSRS, the interviewer will then provide a paper copy of the GIQLI for the patient to complete. This is a 36-question survey containing 5 domains (Core symptoms, physical items, psychological items, social items, and disease items) which each question contains 5 possible answers (which are rated from 0 - 4). Subjects will be asked to review the survey and each question, and circle the associated answer and return the survey to the interviewer. The interviewer will record the responses to each question and scores will be calculated and tracked for each patient longitudinally. The utility of this survey has been demonstrated by an initial assessment of reliability (Eypasch E. *Br J Surgery*. 1995) and has been used in multiple studies to assess any gastrointestinal symptoms and has demonstrated reproducibility.

Safety

Treated Biopsy Proven Acute Rejection (tBPAR)

A treated BPAR is any condition where the subject received anti-rejection treatment and was histologically diagnosed as acute rejection. Renal biopsies will be collected for all cases of suspected acute rejection.

Kidney allograft biopsy

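### The primary GSRS is read out and recorded by an unblinded investigator in a study with no control arm, so an interviewer effect that differs between visits would not cancel

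*Combined protocol and SAP*

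**What the plan says.** **Mode of the primary outcome.** Under Efficacy, Gastrointestinal Symptom Rating Scale (GSRS): "Subjects will be interviewed by one of the investigators, and their responses will be recorded at each time point". The interview is scripted: "The interviewer will be provided a sheet with each of the symptom areas, the associated questions, and the rating scale to conduct the interview". On capture of the answers: "They will ask each question and read each potential response to the patient and circle the associated answer". In support, the section cites an initial study of the scale "which demonstrated validity and strong interrater reliability".

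**Mode of the GIQLI.** The next section reads: "Following completion of the GSRS, the interviewer will then provide a paper copy of the GIQLI for the patient to complete". The patient circles the answers and returns the form to the interviewer. The assessment schedule puts both instruments at the same visits (1, 2, 3, 4 and 6).

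**Blinding and control.** Treatment arms: "This will be a single-arm study". Treatment blinding: "All participants including researchers, subjects, and analysts will be aware of treatment allocation". The only assessor described as blinded is the pathologist who reads the biopsies. The historical cohort is compared on rejection, graft and patient outcomes and infections, not on the GSRS.

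**Analysis.** The GSRS at follow-up is compared with baseline by a paired t-test.

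**Wording on mode.** Purpose and rationale and Study design both describe patients as completing the two surveys, which reads more naturally as self-completion. The GSRS section gives the task first to any member of the study team and then, in the next sentence, to an investigator.

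**The concern.** The GSRS is a subjective symptom score. The person asking the questions knows that every patient has been converted and whether the visit falls before or after conversion. The plan does not keep earlier scores from that person, and it does not fix where the GSRS comes relative to conversation about the drug or adverse events.

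Tone, prompting, or a patient's reluctance to report continuing symptoms to the team that offered the switch could therefore differ between baseline and follow-up. With a concurrent control arm, much of such a difference would appear in both arms and drop out. Here it would enter the mean change and be tested as a drug effect.

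The exposure is partly avoidable, since the protocol already uses patient completion on paper for a secondary outcome at the same visit and gives no reason for treating the primary outcome differently.

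**Working it through.** **Inputs** (Sample size calculation): target change 12 points on the 15-105 scale, SD 18, significance level 0.05, power 80%, dropout 20%. Assumptions: two-sided test, and 18 is the SD of the paired change. The plan states neither.

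**1. Reproduce the plan's figure.** For a paired t-test with n pairs, the noncentrality is δ√n/SD, on n − 1 degrees of freedom.
- n = 19: power 78.5%.
- n = 20: 12 × √20 / 18 = 2.98, power 80.7%. So 20 evaluable patients are needed.
- Dropout: 20 / 0.8 = 25, which is the stated minimum. The assumptions are consistent with the plan.

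**2. Smallest significant mean change.** t(0.975, 19) × 18 / √20 = 2.093 × 18 / 4.472 = 8.4 points.

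**3. What cancels and what does not.** Write the interviewer's effect as c₀ at baseline and c₁ at follow-up. The expected measured change is the true change plus (c₁ − c₀). If c₁ = c₀ the interviewer contributes nothing. Only the difference b = c₁ − c₀ matters.

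**4. Illustration.** The documents give no value for b. With a true change of zero and a shift b toward improvement, the test statistic is noncentral t with noncentrality b√n/18. For n = 20:

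| b (points) | Share of 12-point target | Noncentrality | P(significant improvement) | Two-sided rejection |
|---|---|---|---|---|
| 0 | 0 | 0 | 2.5% | 5.0% |
| 1.5 | 1/8 | 0.37 | 5.4% | 6.5% |
| 3 | 1/4 | 0.75 | 10.5% | 10.9% |
| 6 | 1/2 | 1.49 | 29.3% | 29.4% |

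If the 15-105 range means 15 items scored 1 to 7 (an assumption), 3 points is 3/15 = 0.2 per item.

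**5. Sensitivity to n.** The Population section plans 30 enrolled and 24 completing the year (30 × 0.8). At n = 24 the two-sided rates for 1.5, 3 and 6 points are 6.8%, 12.3% and 34.7%. The table uses 20 because that is the number behind the sample size calculation; the 24 refers to a full year on study drug, not to the primary time point.

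**6. Scale.** The primary-variable section gives the GSRS range as 0-45, not 15-105. The probabilities depend only on b/SD (0.083, 0.167 and 0.333 for the three shifts). In points, they apply only to the 15-105 scale with SD 18.

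**The case against.** The case for leaving the section alone has real weight.

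- **The interviewer transcribes; the patient chooses.** Questions and response options come from a sheet and are read aloud. A reader might infer that an unblinded investigator rates the patient at his or her own judgement. The text does not say that. The script limits the room for influence, though it does not control tone, prompting or what a patient is willing to say aloud.
- **A stable effect cancels.** The mode is the same at every visit, so only a change in the interviewer's effect does harm. This stands, and it narrows the point to the differential part. No severity threshold is set for enrolment, so there is no eligibility reason to inflate baseline scores.
- **Interrater reliability is cited.** This answers less than it seems to. Reliability is agreement between raters, and raters with the same knowledge can agree and share a bias.
- **The GIQLI is a check.** A patient-completed measure at the same visits helps in judging direction. It is secondary, follows the GSRS interview and goes back to the same interviewer, so it is not independent.
- **Self-completion has its own cost.** The cited reliability appears to concern interviewer administration. The documents do not say how the GSRS was given in the study behind the SD of 18, nor whether a self-completed version suits this population.
- **Open label without a control was a deliberate choice**, made on cost and time. The point does not challenge it; the changes proposed fit within that design.

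**Conclusion.** The point holds in limited form. The documents establish the mechanism: an unblinded investigator asks for and records the primary symptom score, and no control arm removes an effect that changes between baseline and follow-up. They do not establish that such an effect exists, or how large it is.

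A reader might infer that the trial's false-positive rate is 11% or 29%, or that a paper form would bring it back to 5%. Neither follows. The rates are consequences of assumed shifts of 3 and 6 points, with SD 18 as the SD of change, a two-sided test and 20 evaluable patients. At 1.5 points the rate is only about 6%. The calculation also treats the whole shift as due to the interviewer, whereas self-completion would leave patient expectation, regression to the mean and natural recovery in place.

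The inconsistent wording on mode and interviewer is a matter of text and needs no assumption. Priority: optional to moderate.

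**What to change.** 1. **Preferred, if a self-completed version suitable for this use is available.** In the GSRS section, have the patient complete the GSRS on paper before contact with the investigator, at baseline and at every later GSRS visit.
2. **Otherwise.** Keep the scripted interview, withhold earlier GSRS scores from the interviewer, and administer the GSRS before any discussion of everolimus or adverse events.
3. **In either case.** State one mode and one interviewer role, in the same terms, in Purpose and rationale, Study design and the GSRS section. Acknowledge that expectation, regression to the mean and natural recovery remain in an uncontrolled before-after change.

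**Cost.** Option 2 needs wording and a fixed visit order, with no extra staff. Option 1 needs a printed form and confirmation that the version is suitable. It departs from the interview mode behind the cited interrater reliability, and the SD of 18 may not carry over exactly. If the 12 points and SD of 18 are kept, the sample size is unchanged at 20 evaluable and 25 enrolled. Whichever mode is chosen should be in place before the first baseline assessment, so that every paired change uses the same mode.
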